### 3 INVESTIGATIONAL PLAN

#### 3.1 Study Design

This study will be a Phase 1, single-center, randomized, double-blind, placebo-controlled design to assess safety and PK of COVID-HIGIV in healthy adults.

Healthy adult subjects are planned to be enrolled and randomized to receive a single dose; see [Table 2](#) below.

Eligible subjects will be randomized 2:2:2:1 to four study treatment arms to receive a single IV infusion of one of three COVID-HIGIV dose levels (1-3) or saline placebo (4), respectively.

**Table 2 Overview of Study Design**

Study Arm	No. of Subjects	Dosing Schedule – Day 1 Visit
1	8	COVID-HIGIV dosage 1*
2	8	COVID-HIGIV dosage 2**
3	8	COVID-HIGIV dosage 3***
4	4	Placebo (saline)

\* 100 mg/kg ( $\approx$ 1 mL/kg), with a maximum of 100 mL COVID-HIGIV for  $\geq$ 100 kg body weight.

\*\* 200 mg/kg ( $\approx$ 2 mL/kg), with a maximum of 200 mL COVID-HIGIV for  $\geq$ 100 kg body weight.

\*\*\* 400 mg/kg ( $\approx$ 4 mL/kg), with a maximum of 400 mL COVID-HIGIV for  $\geq$ 100 kg body weight.

Following randomization and dosing on Day 1, subjects will be kept in the inpatient unit and will be discharged the following day (Day 2 visit). Subjects will be followed for safety and PK up to 84 days (up to Day 85 visit) post-dosing.

Overall study duration for subjects will be up to 91 days (seven days of screening period and 84 days of follow-up post-randomization).

The enrollment/dosing of the first seven subjects (2:2:2:1 randomization) in the study will be staggered, wherein no more than three subjects will be dosed on the same day (dosing at least 1 hour apart). Principal Investigator (PI) and the Sponsor's Medical Monitor (MM) will review blinded data (up to 24 hours after end of IV infusion) before proceeding with dosing subsequent set of staggered subjects. Available safety (blinded) data will be reviewed by Study Monitoring Committee (SMC) (consisting of at least three independent external medical monitors) after seven subjects have completed at least 72 hours of safety follow-up. If unblinding of the safety data is required, closed session by the SMC will be held. An overall decision by the SMC will be made to proceed with full randomization (2:2:2:1) and dosing of the remaining study subjects (n=21). The SMC will perform overall ongoing review of safety data during the study. Study enrollment and administration of study treatments may be temporarily paused by the SMC for safety review, if required (see [Section 8.11](#) for study safety-pausing rules).

Subjects who become positive for SARS-CoV-2 at any time post-dosing follow-up period will be withdrawn from the study (no further specimen collections), but will be followed up for safety only via telemedicine until their originally scheduled last follow-up visit. Subjects who report

clinical signs/symptoms of COVID-19 during telephone contact follow-ups will be classified in severity by site staff as grade 1-4 (see [Appendix II – Grading of COVID-19 Symptoms](#)), while overall clinical status of the subjects with COVID-19 will be assessed by the site staff using modified WHO ordinal scale as outlined (see [Appendix I – Modified WHO Ordinal Scale](#)).

### **3.2 Study Center(s)**

This study will be conducted at a single center in the US.

### **3.3 Sample Size**

There was no formal sample size calculation for this Phase 1 study. However, based on previous experience with hyperimmune globulin products manufactured by Emergent (see [Section 1.2.2](#)) in Phase 1 clinical studies with healthy adults, Emergent deems that the number of subjects planned to receive COVID-HIGIV is sufficient to descriptively assess safety and PK of three COVID-HIGIV dose levels administered by IV to healthy adults.

In total, 28 subjects are planned for the study(8 subjects/dose level, and 4 placebo subjects).

### **3.4 Randomization**

Randomization/dosing of the first seven subjects in the study will be staggered; seven subjects will be randomized 2:2:2:1 (two subjects at COVID-HIGIV dosage level 1, two subjects at COVID-HIGIV dosage level 2, two subjects at COVID-HIGIV dosage 3 and one placebo subject). After the SMC review of the safety data from the first seven subjects, and if the enrollment is recommended to proceed, the remaining subjects (n=21) will be randomized 2:2:2:1.

Randomization list will be generated by a Randomization and Trial Supply Management (RTSM) system vendor. The designated individual at the site receiving the randomization codes will be unblinded (pharmacist). Details on the randomization procedures will be provided in the Pharmacy Manual.

### **3.5 Blinding**

The pharmacy staff assigned to this Phase 1 clinical study will be unblinded to access the randomization assignment and prepare the study treatments. All doses of study treatments will be prepared in the same total volume in the IV infusion bags; in addition, bag covers will be used to mask the bags to maintain the blind.

There will be designated (subcontracted) unblinded clinical study monitors and an independent unblinded Quality Assurance (QA) representative (if needed). In addition, designated personnel at the bioanalytical laboratory who will be assigned to perform PK sample testing may indirectly become unblinded due to nature of test results; however, measures will be implemented not to disseminate bioanalytical laboratory results until required. Other personnel involved in the conduct of the clinical study will remain blinded until database lock and final unblinding.

## Clinical Study Protocol EBS-CVH-003

Version 4.0, 21 Apr 2021

Access to information in electronic data capture (EDC) system will be blinded using role-based permissions. Randomization group and study treatment dispensing data will be provided to Emergent after database lock and unblinding. Dosing data will be reconciled with the randomized treatment group for each subject by the unblinded monitor, and any deviations will be reported in the Clinical Study Report (CSR).

Upon request, subjects who received placebo will be informed of their treatment assignment after all subjects have completed the Day 29 to follow current COVID-19 vaccine recommendations. Placebo recipients will be kept in the study for safety follow-up, but no PK samples will be drawn.

While this is a double-blind study, an unscheduled unblinding may occur at any point after the infusion. Details on the reasons for unblinding and the associated unblinding procedures will be described in the Pharmacy Manual. In an event of unblinding, Emergent must be notified.

## 4 SELECTION OF STUDY SUBJECTS

### 4.1 Subject Inclusion Criteria

Subjects must meet the following inclusion criteria to participate in the study:

1. Able and willing to provide written informed consent (voluntarily signed by the subject) prior to performing any study procedures.
2. Females or males, 18-60 years of age, inclusive.
3. Body mass index (BMI) less than or equal to 35.0 kg/m^2.
4. Women who are either:
  - A) Not of childbearing potential: surgically sterile (at least six weeks post bilateral tubal ligation, bilateral oophorectomy or hysterectomy), or post-menopausal (defined as  $\geq 50$  years of age with a history of  $\geq 12$  months without menses prior to randomization in the absence of other pathologic or physiologic causes, following cessation of exogenous sex-hormonal treatment); OR
  - B) Women of childbearing potential (WOCBP) who are not planning to be pregnant during the study period and meet all of the following criteria:

Negative pregnancy test prior to randomization/dosing at Day 1; **and**

Use of a highly effective contraception during the study period:

- Hormonal contraceptives (e.g., implants, pills, patches) initiated  $\geq 30$  days prior to Day 1; or
- Intrauterine device (IUD) inserted  $\geq 30$  days prior to Day 1; or
- Double barrier type of birth control (e.g., male condom with female diaphragm, male condom with cervical cap).

5. Subject understands and agrees to comply with planned study procedures.
6. Healthy as determined by principal investigator based on medical history, physical exam, vital signs, urinalysis, blood chemistry and hematology test results at Screening and no evidence of prior exposure to SARS-CoV-2 (i.e., RT-PCR negative for SARS-CoV-2 and negative for SARS-CoV-2 antibodies) at Screening.

### 4.2 Subject Exclusion Criteria

Subjects who have any of the following exclusion criteria will be excluded from the study:

1. Use of any investigational product within 30 days prior to Screening or use of any SARS-CoV-2 vaccines or monoclonal antibodies, or COVID-19 convalescent plasma at any time prior to Screening or during study follow-up period, or subject plans to participate in another clinical study during the study period.

2. Screening clinical laboratory test result greater than the laboratory's upper limit of normal (ULN) for alanine aminotransferase (ALT), aspartate aminotransferase (AST), random glucose, total and/or bilirubin, blood urea nitrogen (BUN), or creatinine. Other serum chemistry parameters that are not within the reference range will not be considered exclusionary unless deemed clinically significant by the principal investigator.
3. History of hypersensitivity to blood or plasma products or to COVID-HIGIV excipients (proline, PS80).
4. History of allergy to latex or rubber.
5. History of hemolytic anemia.
6. History of IgA deficiency.
7. Receipt of any blood product within the past 12 months.
8. Plasma donation within 7 days or significant blood loss or blood donation within 56 days of randomization/dosing.
9. History of known congenital or acquired immunodeficiency or receipt of immunosuppressive therapy (e.g., prednisone or equivalent for more than two consecutive weeks within the past three months).
10. History of thrombosis or hypercoagulable state with increased risk of thrombosis.
11. History of clinically significant chronic illness (e.g., requiring hospitalization in the past three months) such as cardiac, pulmonary, renal, hepatic or other chronic conditions.
12. Receipt of a live vaccine within 28 days prior to screening or anticipated receipt of a live vaccine during the study period.
13. Currently pregnant, breastfeeding, or planning to become pregnant during the study.
14. History of, or suspected substance abuse problem (including alcohol).
15. Other medical condition which may place subject at increased risk due to participation in the study as determined by the investigator.
16. Any planned elective surgery or procedure during the follow-up period that impacts study compliance.
17. An opinion of the investigator that it would be unwise to allow the individual to be randomized into the study.

#### 4.3 Subject Withdrawal

The subjects must be available, without coercion, for all parts of the study. If continued participation jeopardizes the subject's health, the subject should be withdrawn from the study. The investigator is encouraged to consult Emergent prior to the withdrawal of any subject, except in the event of a medical emergency. The reason for withdrawal of any subject must be

clearly documented on the study source documents and the appropriate Electronic Case Report Form (eCRF).

#### **4.3.1 Subject Withdrawal Criteria**

All subjects are free to withdraw from participation in this study at any time, for any reason, specified or unspecified, and without penalty or loss of benefits to which the subject is otherwise entitled. In addition, subjects may be withdrawn from the study for any of, but not limited to, the following reasons:

- The subject develops an intercurrent illness that prevents completion of the study.
- The subject becomes positive for SARS-CoV-2 at any time post-dosing.
- It is the opinion of the principal investigator that it is unwise for the subject to continue in the study.
- The subject is not compliant with the requirements of the study to the satisfaction of the investigator and/or sponsor (e.g., non-cooperative, misses appointments, unreported use of concomitant medications).
- The subject is lost to follow-up.

If a subject is withdrawn from the study, they will not be re-entered into the study for any reason.

#### **4.3.2 Subject Replacement**

Subjects withdrawn from the study or who withdraw consent after randomization will not be replaced.

#### **4.3.3 Follow-up for Withdrawn Subjects**

Every attempt will be made to ensure that subjects who are withdrawn, or who withdraw from the study during the active treatment or follow-up period, will complete all safety and available assessments for the Withdrawal Visit (WV) visit as outlined in this protocol; see [Table 1](#) or [Section 6.3.3](#) for a list of recommended WV assessments. The investigator should inform the subjects that these assessments are for their own safety.

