### 2.3 Study Endpoints

#### 2.3.1 Primary Endpoints

The following primary safety endpoints will be evaluated:

- AEs within 72 hours post-dosing.
- AEs leading to discontinuation or temporary suspension of infusion.
- AEs and SAEs in healthy adults up to 84 days post- administration of a single COVID-HIGIV dose.

The following primary PK endpoints (based on PK sample test results of an immunobinding IgG assay and a pseudovirus neutralization assay) will be evaluated in healthy adults:

- Primary PK Endpoints (at each of the three COVID-HIGIV dose levels):
  - $AUC_{0\text{-last}}$ : area under the concentration-time curve from time 0 to the last quantifiable concentration after dosing.
  - $AUC_{0\text{-inf}}$ :  $AUC_{0\text{-last}}$  plus the additional area extrapolated to infinity after dosing.
  - $AUC_{0\text{-14d}}$  after dosing.
  - $AUC_{0\text{-28d}}$  after dosing.
  - $C_{\max}$ : maximum observed concentration after dosing.
  - $T_{\max}$ : time at which  $C_{\max}$  occurs after dosing.
  - $C_{\min 28d}$ : observed or estimated concentration at 28 days after dosing.
  - $\lambda_z$ : terminal elimination rate constant after dosing.
  - $T_{1/2}$ : apparent terminal elimination half-life after dosing.

- CL: systemic clearance after dosing.
- $V_Z$ : volume of distribution after dosing.

**Secondary PK Endpoints:** following body weight normalized PK parameters will be estimated as PK parameter divided by subject body weight (kg) at baseline.

- CmaxBWN: Body weight normalized Cmax
- Cmin28dBWN: Body weight normalized Cmin28d
- $AUC_{0-14d}BWN$ : Body weight normalized  $AUC_{0-14d}$
- $AUC_{0-28d}BWN$ : Body weight normalized  $AUC_{0-28d}$
- $AUC_{0-last}BWN$ : Body weight normalized  $AUC_{0-last}$
- $AUC_{0-inf}BWN$ : Body weight normalized  $AUC_{0-inf}$

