## 8 ASSESSMENT OF SAFETY

The safety of COVID-HIGIV will be assessed by collection of adverse events (AEs), laboratory test results (blood chemistry and hematology, urinalysis), concomitant medications, medical history updates, vital signs and physical exam results.

The occurrence of AEs will be monitored throughout all phases of the study and will cover all participating subjects. Any medical history changes that occur after baseline (Day 1) but before dosing will be updated as medical history. Capture of AEs starts during IV infusion of study treatment and until the end of study period (up to Day 85 visit). Unanticipated problems related to study procedure may be collected following enrollment.

Adverse events are to be elicited by the investigator (or designate) by asking the subject non-leading questions. The association of the AE to COVID-HIGIV is to be judged by the investigator as related or unrelated (see Section 8.3 below).

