### 6.5.2 Missing Outcomes and Covariates

Subjects with missing numeric data are treated as missing completely at random (MCAR) when calculating summary statistics.

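### Safety contacts to Day 85 continue only for subjects withdrawn for a positive SARS-CoV-2 test; for other investigator- or sponsor-initiated withdrawals, new AEs and SAEs are not solicited after at most one Withdrawal Visit, although the primary endpoint runs to 84 days.

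*Protocol*

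**What the plan says.** One primary safety endpoint in Protocol 2.3.1 is "AEs and SAEs in healthy adults up to 84 days" after the single dose. Protocol 8 sets the collection period to match: "Capture of AEs starts during IV infusion of study treatment and until the end of study period (up to Day 85 visit").

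The rules after withdrawal differ by reason:

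- **Positive SARS-CoV-2 test (Protocol 3.1).** Specimens stop, but these subjects "will be followed up for safety only via telemedicine until their originally scheduled last follow-up visit".
- **All withdrawals (Protocol 4.3.3).** Every attempt is to be made so that withdrawn subjects "will complete all safety and available assessments for the Withdrawal Visit (WV) visit as outlined in this protocol". Protocol 6.3.4 limits that visit to withdrawals falling outside a scheduled visit or window. No later contact is scheduled.

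The reasons in Protocol 4.3.1 include non-compliance, investigator opinion and this one: "The subject develops an intercurrent illness that prevents completion of the study". None carries its own follow-up rule there.

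Withdrawn subjects are not replaced (4.3.2). SAP 5.2 keeps every dosed subject in the Safety Set. SAP 6.1 and 9.2.1 summarise AEs as counts and percentages of subjects.

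**The concern.** This is a single-dose study. Once the infusion is over, no later treatment makes post-withdrawal safety data irrelevant, and a dosed subject's 84-day window is as informative after withdrawal as before it. The protocol accepts this for SARS-CoV-2 positives (3.1), for placebo recipients unblinded for vaccination (3.5) and for other unblinded subjects (8.10). All of these are kept, or asked to stay, under safety follow-up. A subject withdrawn by the investigator for another reason is left out, and no reason is stated.

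At stake is completeness of new-event capture for a primary endpoint. An event that nobody asks about cannot enter the numerator, while the subject stays in the denominator. The error therefore runs in one direction. A late SAE missed this way would also not reach the Study Monitoring Committee, although Protocol 8.11 lets one SAE trigger a pause review.

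**Working it through.** **1. The plan's own figures.** Four blocks of 7 at 2:2:2:1 give 8 + 8 + 8 + 4 = 28 subjects, as stated in Protocol 3.3. The stated duration is 7 + 84 = 91 days. Both reproduce. No dropout or withdrawal rate is given.

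**2. Does any other section fill the gap?**

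| Section | What it continues after withdrawal | Solicits new AEs to Day 85? |
|---|---|---|
| Protocol 3.1 | Telemedicine safety contacts, SARS-CoV-2 positives | Yes, that group only |
| Protocol 4.3.3 and 6.3.4 | At most one Withdrawal Visit | No |
| Protocol 8.8 | AEs and SAEs already identified | No |
| Protocol 8.6.1 | Pregnancies, to outcome | No |
| Protocol 3.5 and 8.10 | Unblinded subjects, who are not withdrawn | Not applicable |
| Protocol 8.5 | 24-hour telephone number for subjects | No, the subject must call |

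**3. Does the analysis allow for shorter observation?** SAP 9.1 defines exposure by volume, dose and potency, not follow-up time. SAP 9.2 has no censoring rule and no rate per subject-day. SAP 5.4 puts Early Withdrawal on the same analysis time point as Day 85. SAP 7.1 tabulates withdrawals and lists disposition by subject, but does not call for the last day on which AEs were asked about.

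**4. Observation lost by one such withdrawal.** The withdrawal day is an assumption. Days lost = 84 − (Day − 1). The share of an arm's planned subject-days is days lost / (84 × n). The last column counts the scheduled visits that remain.

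| Withdrawn on | Days lost | Share of subject's window | Share, arm of 8 | Share, placebo arm of 4 | Contacts left |
|---|---|---|---|---|---|
| Day 8 | 77 | 91.7% | 11.5% | 22.9% | 6 |
| Day 15 | 70 | 83.3% | 10.4% | 20.8% | 5 |
| Day 29 | 56 | 66.7% | 8.3% | 16.7% | 3 |
| Day 57 | 28 | 33.3% | 4.2% | 8.3% | 1 |

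**5. Effect on crude incidence.** Assume a constant hazard, one subject withdrawn on Day 29, and withdrawal unrelated to risk. With true 84-day risk p, the risk to 28 days is q = 1 − (1 − p)^(28/84). The expected crude incidence is ((n − 1)p + q)/n.

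| p | q | n = 8 | n = 4 |
|---|---|---|---|
| 15% | 5.3% | 13.8% | 12.6% |
| 30% | 11.2% | 27.7% | 25.3% |
| 50% | 20.6% | 46.3% | 42.7% |

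For example, (7 × 0.15 + 0.053)/8 = 0.138. The expected shortfall is 1.2 to 3.7 percentage points in an arm of 8 and 2.4 to 7.3 in the placebo arm. The values of p are assumptions. 15% is the top of the adverse-reaction range that Protocol 1.2.2 gives for immunoglobulin products.

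**The case against.** The other side has several sound points.

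- **An ill subject is already counted.** A reader might infer that someone withdrawn for illness stays in the tables as event-free. The documents do not support that. Under Protocol 8.1.1 and 8.5 a new illness after dosing is itself an AE and goes on the AE form whatever its cause. The subject is in the any-AE numerator, and in the SAE numerator if the illness is serious. Only a later, different event can be missed.
- **Contact does not stop altogether.** Protocol 8.8 follows open AEs actively for up to 30 days beyond the last visit, and follows SAEs until they are resolved or stable, or the subject is referred. It would be wrong to say that withdrawn subjects are never asked anything again. What is missing is scheduled solicitation of new events.
- **The missing-data sentence is not evidence.** SAP 6.5.2 says "Subjects with missing numeric data are treated as missing completely at random (MCAR) when calculating summary statistics". A reader might take this as the SAP's assumption for AE follow-up, but it concerns numeric data, not counts of subjects with events.
- **The size is unknown.** One subject in an arm of 8 is 1/8 = 12.5 percentage points, but that holds for any single event and shows no effect of this rule. The constant hazard in the working is also unfavourable to the plan: Protocol 1.2.2 places the common reactions during the infusion and the hours after it.
- **The asymmetry may be deliberate.** Protocol 1.2.2 commits to watching for disease worsening because of possible antibody-dependent enhancement, which would explain longer follow-up of infected subjects.
- **The avoidable group is narrow.** Withdrawal under 4.3.1 is discretionary, and some non-compliant subjects may not answer further calls.

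These points limit the size and wording of the concern. They do not close the gap. A reason to follow infected subjects is not a reason to stop asking the others, and none of the sections above schedules contact to find a new event.

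**Conclusion.** The gap is real and its direction is known. For a dosed subject withdrawn by the investigator or sponsor for a reason other than a positive SARS-CoV-2 test, new-onset AEs and SAEs are not solicited through Day 85, so the 84-day incidence can only be understated. The endpoints for 72 hours and for infusion interruption are largely unaffected, because subjects stay in the unit for 24 hours and Day 4 follows soon after.

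The size cannot be fixed from the documents, since no number of withdrawals is given and it may be small in 28 healthy adults. The shortfalls in the working are illustrations. They fit best a subject withdrawn for non-compliance or investigator opinion who has had no AE; for an illness withdrawal, the any-AE count is already right and only the tables by term, severity or seriousness could be short. Illness withdrawals may be linked to safety, so the loss may be informative, but the documents do not establish that.

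A reader might also infer that the SAP declares withdrawn subjects observed to Day 84. It does not say so; this follows only from the absence of any rule for shorter follow-up. The aims are descriptive and no hypothesis is tested, so this is an inexpensive improvement to a primary safety endpoint, not a flaw that invalidates the study.

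**What to change.** **Protocol 4.3.3 and synopsis.** Extend the telemedicine safety contacts of 3.1 to every dosed subject withdrawn for any reason other than withdrawal of consent or loss to follow-up. Collect AEs, SAEs and concomitant medications at the remaining scheduled contacts to Day 85, with no specimens.

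**SAP 7.1 or 9.2.** Add a listing of the last AE-contact day for each subject whose AE collection ended early. This is worth doing even if the protocol cannot be amended, because it shows which 84-day percentages rest on shorter observation.

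**Wording to reconcile in the same edit.** Protocol 4.3.3 points to 6.3.3 (the Day 85 visit) for assessments that are in 6.3.4. Protocol 3.1 makes withdrawal after a positive test definite, while 4.3.1 and SAP 2.2 make it optional. SAP 2.2 also allows home healthcare visits where 3.1 describes telemedicine only.

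**Cost.** Protocol wording, one SAP listing, and per withdrawn subject between one remote contact (withdrawal on Day 57) and six (withdrawal on Day 8), through a route already set up for SARS-CoV-2 positives. The sample size does not change.
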